Nasopharyngeal swab samples will be taken for quantitative real-time polymerase chain reaction to make diagnosis of Covid19 (2 repeated tests).

Data collected include time of type of symptoms (cough, fever, dyspnea, conjunctivitis, diarrhea, asthenia, arthralgia) and duration, comorbidities (presence of diabetes, hypertension, cardiovascular disease), PaO2/FiO2 ratio, age, sex, height, weight, triglycerides, complete blood count, D-dimer, lactic acid dehydrogenase (LDH), high-sensitivity C-reactive protein (hs-CRP), albumin, and ferritin. The duration of the follow-up will be 28 days from the patient's hospitalization or until his/her discharge or death.

Primary end-point

The primary end-point is to identify the best predictors of critical coronavirus pneumonia and to realize a simple severity score able to early classify high-risk individuals admitted to Internal Medicine Department for COVID-19 disease, needing an intensive approach.

The evaluated predictors for the score assessment are the following: symptoms duration, type of symptoms (cough, fever and dyspnea), comorbidities (presence of diabetes, hypertension, ischemic heart disease), PaO2/FiO2 ratio, age, sex, body mass index (BMI), triglycerides, white cell count, lymphocyte count, D-dimer, lactic acid dehydrogenase (LDH), high-sensitivity C-reactive protein (hs-CRP), albumin, and ferritin. These parameters were collected at admission.

Sample size calculation

The sample size determination is based on the following considerations:

1) the objective of the study is that of finding the best predictors of severe coronavirus pneumonia outcome;

 the study sample will be constituted by inpatients cases of COVID-19 admitted to Internal Medicine Department of Fondazione Policlinico A. Gemelli IRCCS;

3) in order to test the predictive ability of the developed score the study sample will be split into a fitting population and a validation population by using the internal/validation/data-splitting method 4) the following rule-of-thumb will be considered: the power for a test of a medium-sized partial correlation between y and a predictor, holding all other predictors constant, is approximately .80 if N = 104 + m, where m is the number of predictors (11).

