Starting from the above considerations, and from the hypothesis that about 20 predictors will be evaluated for development of a risk score able to predict the severe coronavirus pneumonia outcome, the population size of the fitting population is set to N = 104+20=124 patients. In the procedure of splitting the data set into a fitting population and a validation population, the 50% of the entire sample will be used for the fitting step and the remaining 50% will be used as a validation population. A sample size of 248 patients will be therefore necessary.

Statistical Analysis

Primary Analysis

The data set will be split into a fitting population and a validation population by using the internal/validation/data-splitting method. The internal/validation/data-splitting method is chosen to limit the possible increase in bias that can occur with other techniques for internal validation such as

Bootstrapping technique if the original study population contains biases. The portion of the population used as fitting population for model development will be chosen randomly. The model will be then tested, in terms of its performance on the remaining validation population. Computation of the C statistic will be used to indicate the discrimination performance of the model. The C statistic represents a measure of the model's performance in terms of the model discrimination ability to separate subjects with different outcomes, and for the logistic model, it is equivalent to the area under the curve of the receiver operating characteristic (ROC) curve associated to the model (12) Values of C between 0.8 and 0.9 will be considered to give an excellent discrimination.

Computation of the probabilities: For each subject, both from the fitting population and the validation population, the probability of the studied outcome will be computed on the basis of the patient's covariate values. Each subject will be therefore characterized by the values of the covariate set, the outcome (coronavirus-severity, 0/1) and by the estimated probability of the outcome.

Computation of the C statistics: For both the fitting and the validation populations, the C statistics will be computed. The accuracy (percentage of true positive and negative on the total subjects) of the prediction model will be also computed.

Procedure repetition: The entire procedure (data splitting, model fitting, probability computation) will be repeated 200 times.

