Model fitting onto the whole population: The model will then be fitted using all the original data.

Results analysis: At the end of the procedure, the distribution of different indicators will be computed: for each variable, frequency histograms of the estimated coefficients along with their associated standard errors and levels of significance will be plotted. The importance index of each variable computed from each data splitting and model fitting will be also plotted.

The estimated coefficients from the whole population will be compared with the respective distributions (they should be centred around the estimates obtained on the whole sample); the distribution of the variability of the model coefficients indicates to which extent the results are dependent from the subpopulation used; comparison between the distribution of the C statistic computed on the fitting and the validation sample, along with the distribution of their Delta provide indication of the discrimination power of the model. It is expected that the C statistic is larger for the fitting sample than for the validation sample. A model with a high discrimination power presents small drops in the values of the C statistic when computed on the validation sample with respect to

values computed on the fitting sample for which the values are expected to be larger (C Delta distribution centred around the zero).

On the basis of the obtained results on the full model, the entire procedure is repeated on the subset of the most important variables to test and validate the final reduced model including the most meaningful predictors. Once the model validation is assessed the fitted coefficients used to compute the probability of the outcome on a generic patient will be those obtained from the "reduced model" fitting on the whole population sample.

Secondary analyses

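### C, accuracy and Delta describe 124-patient fits but the delivered score is a 248-patient fit: pessimistic for the full model, outweighed by selection on all patients for the reduced one

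*Combined protocol and SAP*

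**What the plan says.** Sample size calculation sets the fitting half from a rule of thumb: "the population size of the fitting population is set to N = 104+20=124 patients". It then doubles this: "the 50% of the entire sample will be used for the fitting step and the remaining 50% will be used as a validation population", and "A sample size of 248 patients will be therefore necessary".

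Under Statistical Analysis, Primary Analysis, the model is built on one random half and tested on the other. "For both the fitting and the validation populations, the C statistics will be computed", accuracy is added, and "The entire procedure (data splitting, model fitting, probability computation) will be repeated 200 times". A C between 0.8 and 0.9 is to be called excellent. Delta is the drop in C from fitting half to validation half, and a distribution centred on zero is read as good discrimination.

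The Results analysis paragraph then uses the full-model results to pick a subset of important variables and repeats the splitting on that subset. The sentence that begins "Once the model validation is assessed the fitted coefficients used to compute the probability of the outcome on a generic patient" goes on to say that these coefficients come from the reduced model fitted to the whole sample.

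**The concern.** No model fitted to 124 patients is ever used on a patient. With about 20 candidate predictors and a binary outcome, a 124-patient fit overfits more than a 248-patient fit. Validation figures from halves therefore describe a weaker model than one fitted to everybody. Repeating the split 200 times averages out the luck of a single split but leaves this bias in place. The plan neither says that its figures refer to half-size fits nor corrects for it.

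A second feature pulls the other way. The reduced model's variables are chosen once, from results that draw on all 248 patients. Every patient later held out in a validation half has already helped to choose the variables being tested.

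At stake is the study's main performance result. C may be labelled excellent, or denied that label, because of the validation scheme. Delta may mislead on overfitting, and the direction of the error differs between the two models the plan reports.

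**Working it through.** **The plan's own figures.** N = 104 + m with m = 20 gives 124, and 124 / 0.5 = 248. Both reproduce exactly. (Counting the predictors listed under Primary end-point gives 19, hence 123 and 246; the difference is immaterial here.)

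**Inputs the documents do not give.** These are the study's expected event rate, the best achievable C, the effect pattern, the importance index and the number of variables kept. All were assumed. The only severity rates in the Introduction come from a cited Chinese cohort: 10.1% severe at admission, and 15/66 = 22.7% progressing. Simulations covered event rates of 10% to 40% and best achievable C of 0.70 to 0.87, with independent and with correlated predictors.

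**Method.** Cohorts of 248 were simulated from a logistic model with 19 or 20 predictors. For each cohort:
- split Delta = mean C in fitting halves minus mean C in validation halves;
- true optimism = apparent C of the 248-patient fit minus its C in a large independent population;
- error = mean validation C minus that independent-population C.

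**Worked case.** Best C 0.80, event rate 20%, 20 independent predictors (10 without effect), 200 cohorts, 20 half-splits each, variables ranked using all 248 patients. Errors and ratios were computed before rounding; the standard error of the error column is 0.003.

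| Variables kept | Validation C (halves) | True C, 248-patient fit | Error | Split Delta | True optimism | Ratio |
|---|---|---|---|---|---|---|
| 20 (full model) | 0.723 | 0.762 | -0.038 | 0.176 | 0.093 | 1.88 |
| 15 | 0.749 | 0.762 | -0.013 | 0.138 | 0.090 | 1.53 |
| 10 | 0.775 | 0.762 | +0.014 | 0.093 | 0.082 | 1.13 |
| 8 | 0.781 | 0.762 | +0.019 | 0.075 | 0.074 | 1.01 |
| 5 | 0.778 | 0.756 | +0.022 | 0.050 | 0.058 | 0.86 |
| 3 | 0.760 | 0.740 | +0.021 | 0.031 | 0.043 | 0.73 |
| 5, fixed in advance | 0.767 | 0.780 | -0.013 | 0.047 | 0.022 | 2.14 |

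For the full model, Delta = 0.899 - 0.723 = 0.176, against a true optimism of 0.855 - 0.762 = 0.093. The last row shows the half-size effect without any selection leak. The sign of the error changes between 10 and 15 variables kept.

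**Across scenarios: error in C.**

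| Scheme | Full model | Reduced, chosen once on all 248 | Reduced, chosen anew in each training set |
|---|---|---|---|
| 50/50 halves | 0.02-0.07 too low | 0.01-0.07 too high | 0.03-0.08 too low |
| 10-fold | 0.01-0.04 too low | 0.01-0.06 too high | 0.005-0.04 too low |

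Full-model Delta was 1.6-2.1 times the true optimism. For the reduced model as written, with 3 to 10 variables kept, the ratio was about 0.6-1.2. With six variables chosen afresh in each half, it was 2.0-2.7; with 10-fold, 1.3-1.5.

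**Effect on the label.** At best C 0.87 and event rates from 10.1% to 35%, a six-variable model fitted to 248 patients truly scored 0.815-0.840. Halves with selection inside would report about 0.74-0.81, falling below 0.80 at 10.1%, 15% and 22.7%.

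**The case against.** A reader might infer that the half-size fits make the reported C conservative, and Delta about double, for the model patients would get. The documents do not support this. That model is the reduced one, and Results analysis has its variables chosen from results on all 248 patients before the splitting is repeated. In the simulations this leak more than cancels the half-size penalty unless most predictors are kept, and the stated aim is a simple score. For the delivered model the likelier failure is overstated discrimination.

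It can also be objected that fold size then makes no difference. As far as it goes, this stands: going to 10-fold without repeating selection left the reduced model's C 0.01-0.06 too high, no better than halves. But the natural repair of the leak, reselecting within each half, exposes the half-size penalty in full.

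The plan justifies data-splitting as a protection against bias in the source sample. Random halves of one cohort share that bias just as cross-validation folds do, so the argument does not favour halves.

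Three further points stand in part. Pessimism from split samples is a familiar trade-off. The 0.8-0.9 band is a label to which the plan attaches no decision. And with five predictors fixed in advance, C is only 0.00-0.01 too low. These limit the gravity of the point but do not remove the mismatch.

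**Conclusion.** The mismatch is plain in the text: performance is measured on 124-patient fits, and the delivered coefficients come from 248. Its consequence depends on the model. For the full model, C is too low and Delta is inflated. For the reduced model as written, with about 3-10 variables kept, the net error in C is upward and Delta is roughly right or too small. Only with 15 of 20 variables kept did the net error turn slightly downward, by 0.005-0.013.

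The sizes rest on assumed event rates, effect patterns and numbers of retained variables, so they should be read as ranges. The directions for the full model and for a short reduced model agreed across independent and correlated predictor designs. The validation scheme should be changed before analysis, with training size and selection handled together; correcting either one alone leaves a material error.

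**What to change.** - For C, accuracy and Delta of both the full and the reduced model, replace the 50/50 splits with 20 repeats of 10-fold cross-validation on all 248 patients. Each fit then uses 0.9 x 248, about 223 patients, with about 25 held out.
- In every fold repeat the whole procedure, including the choice of variables. This requires the selection rule to be written so that a program can apply it.
- Compute C and accuracy from the held-out predictions. Define Delta as the apparent C of the 248-patient fit minus the cross-validated C.
- Keep the 200 half-splits only for the coefficient and importance histograms.
- Take the confidence interval for C from a patient-level bootstrap that keeps all copies of a patient in the same fold. The 20 repeats overlap heavily, so their spread is not an error bar.

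Cost: plan wording and code, with no extra patients. There are 20 x 10 = 200 extra runs of the modelling procedure beside the retained half-splits, plus the bootstrap. More fits are needed if the selection rule itself uses repeated splits within each fold. The 200-value Delta distribution is given up. Some pessimism remains, up to about 0.04 in C at a 10% event rate.

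### C between 0.8 and 0.9 is labelled 'excellent' with no interval, although with 248 patients the 95% interval at C = 0.80 is at least about as wide as that band

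*Combined protocol and SAP*

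**What the plan says.** The only numerical yardstick for the score's performance is in Statistical Analysis, Primary Analysis: "Values of C between 0.8 and 0.9 will be considered to give an excellent discrimination". No confidence interval, standard error or lower limit for C is specified anywhere. The plan also does not say which C the label applies to: one split, the average over splits, or the refit on all patients.

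The split, fit and evaluation are repeated 200 times. Under Results analysis, the output is read through a "comparison between the distribution of the C statistic computed on the fitting and the validation sample", together with the distribution of the difference (Delta) between the two. That paragraph does not return to the 0.8–0.9 band.

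The sample size rests on a rule under which power for a medium-sized partial correlation "is approximately .80 if N = 104 + m, where m is the number of predictors". From this, "the population size of the fitting population is set to N = 104+20=124 patients", and the 50/50 split doubles it: "A sample size of 248 patients will be therefore necessary". No expected rate of severe outcome is given.

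The final score is a reduced model. Its predictors are picked for importance from the full-model results, the splitting is then repeated on that subset, and the coefficients come from a fit to all patients.

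**The concern.** The precision of C depends mainly on the number of patients with the event. The sample-size rule concerns a different quantity and uses no event rate, so nothing in it secures a usefully precise C. If the interval is as wide as the band, an observed value inside the band does not separate a score that belongs there from one that lies clearly below it.

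The split distributions do not settle this as the plan uses them. A small Delta shows little optimism; it does not show that C is precisely known. All 200 splits also reuse the same 248 patients. At stake is how a single-centre score, meant for classifying high-risk inpatients, is described to those who may use it.

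**Working it through.** **The plan's own figure.** 104 + 20 = 124 for the fitting half; 124 / 0.50 = 248 in total. Both reproduce. C does not enter.

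**Inputs.** N = 248 (Sample size calculation). Band 0.80 to 0.90, width 0.10 (Primary Analysis). The event rate is an assumption, taken from 10% to 50%. The Introduction gives two figures from a cited cohort that help to place it: 10.1% severe at admission, and 15 of 66 (22.7%) progressing in hospital. Neither is offered as the expected rate for this study.

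**Formula (Hanley–McNeil).** With n1 events, n0 non-events, Q1 = C/(2 − C) and Q2 = 2C²/(1 + C):

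SE² = [C(1 − C) + (n1 − 1)(Q1 − C²) + (n0 − 1)(Q2 − C²)] / (n1·n0)

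**Example, C = 0.80, 22.7% events (n1 = 56, n0 = 192).** Q1 − C² = 0.6667 − 0.64 = 0.0267; Q2 − C² = 0.7111 − 0.64 = 0.0711.
SE² = [0.16 + 55 × 0.0267 + 191 × 0.0711] / 10,752 = 15.21 / 10,752 = 0.001415, so SE = 0.0376 and 1.96 × SE = 0.074.

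**All 248 patients, C = 0.80.**

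| Assumed event rate | Events | SE | 95% half-width | Full width |
|---|---|---|---|---|
| 10% | 25 | 0.0545 | 0.107 | 0.214 |
| 15% | 37 | 0.0453 | 0.089 | 0.178 |
| 20% | 50 | 0.0395 | 0.077 | 0.155 |
| 22.7% | 56 | 0.0376 | 0.074 | 0.147 |
| 50% | 124 | 0.0282 | 0.055 | 0.110 |

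At C = 0.85 the full width runs from 0.193 (10%) to 0.097 (50%). At C = 0.90 it runs from 0.164 to 0.080, so only near the top of the band, with many events, is it clearly narrower than 0.10. In one 124-patient validation half, the half-width at C = 0.80 is 0.154, 0.110 and 0.104 at 10%, 20% and 22.7%. The formula treats the score as fixed and omits the variability from refitting.

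**What re-splitting does.** Repeated 50/50 splits of 248 patients were simulated (assumed: five fixed predictors, 23% events, 150 data sets, 200 splits each). Between simulated studies, the SD of C was 0.053 for a single split and 0.040 for the mean over splits. Averaging therefore helps, but the mean keeps a 95% spread of 3.92 × 0.0396 = 0.155, close to the 0.147 above. The SD over splits within a study averaged 0.036, near the between-study SD. Dividing it by √200 = 14.1 would give an interval about 14 times narrower than the undivided SD gives.

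**Whether the split SD can supply the interval.** This depends on where predictors are selected. One simulation set assumed 20 candidates, ten with equal effects, and kept five by |z| on all 248 patients before re-splitting (200 data sets, 60 splits each). Mean validation C was 0.03 to 0.07 above the delivered model's C in new patients, and mean ± 1.96 × split SD covered that C in 68–83% of studies. A second set, again selecting on all 248 patients first, gave 0.01 to 0.06 too high and 68–89% coverage, nearly all misses being too high. In that second set, coverage was 94–95% with predictors fixed in advance, and 93–98%, erring low, with selection repeated inside each fitting half.

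**The case against.** The plan is not silent on uncertainty. A reader might infer that the score would be reported with no sign of it, but Results analysis calls for the distribution of C over 200 splits, and its SD is numerically close to the sampling SD when predictors are fixed. This stands: what is missing is an interval and its link to the label, not the raw material.

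A reader might also infer that the study's verdict turns on reaching 0.80. The documents do not support that. The band is an interpretive convention on which no decision depends; the model is also judged on Delta, coefficient stability and accuracy.

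Nor does re-splitting achieve nothing: it lowers the error relative to one split, though not below the limit that 248 patients set.

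A headline that C = 0.80 is compatible with anything from about 0.70 to 0.90 needs roughly 10% events. At 22.7% the range is about 0.73 to 0.87 (0.80 ± 0.074). Mislabelling rates computed for scores within a few hundredths of 0.80 say little about clearly poor or clearly good scores, because any cut misclassifies its near neighbours.

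Finally, demanding that the lower limit clear 0.80 would be a choice about burden of proof that the plan does not make. At 22.7% events it would require an observed C of about 0.864 on 248 patients. Reporting the interval is enough.

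**Conclusion.** The point holds as a reporting gap. The plan attaches a favourable label to C without an interval, at a sample size not chosen for the precision of C. At C = 0.80 the approximate 95% interval on all 248 patients is 0.110 to 0.214 wide over assumed event rates of 50% down to 10%, against a band of 0.10. Averaging over re-splits of the same patients cannot remove that error.

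The size rests on the assumed event rate and on a formula that ignores refitting. The coverage results rest on simulation settings that the documents do not fix. The documents do not support the stronger conclusions that uncertainty is wholly unreported or that the study's success depends on the 0.80 limit.

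**What to change.** In Primary Analysis, state that the label refers to the validation C of the final model, that this C is reported with an approximate 95% interval next to any use of 'excellent', and that the report says so when the interval extends below 0.80.

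Obtain the interval in one of two ways:

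- Repeat predictor selection inside each of the 200 fitting halves, then take the mean ± 1.96 × the SD of the 200 validation C values, not divided by √200.
- Bootstrap the whole procedure, including selection.

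Do not take it from re-splits of a predictor set already selected on all patients: that interval is centred too high and under-covers.

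The cost is some extra computation and SAP wording; no further patients or data are needed. The validation C may come out lower and slightly conservative, and the statement of performance will be less favourable.

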A similarity between cytokine profile of COVID-19 disease and secondary haemophagocytic syndrome (sHLH) has been reported (4). Therefore, it was suggested to screen all patients with severe COVID-19 infection both for hyperinflammatory markers (like ferritin), and the HScore commonly used to generate a probability for diagnosis of sHLH (8), which includes some laboratory parameters like triglycerides, fibrinogen, ferritin, serum aspartate aminostransferase (8).

A recent retrospective analysis on 487 COVID-19 Chinese patients admitted to Hospital, showed that the 49 (10.1%) severe cases at admission, was elderly, more commonly male and had a higher incidence of hypertension. Therefore, the Authors defined a host risk score on the basis of the three risk factors, aimed to assess the intrinsic host susceptibility to develop severe cases of COVID-19. This score was also validated in 15 out of 66 patients with a mild to moderate presentation of disease at admission, who showed a progression of disease during hospital stay within a median follow-up time of 15 days (9).

Another work by Zhou et al. on 191 Chinese COVID-19 patients showed that older age, D-dimer levels greater than 1 μ g/mL, and higher SOFA score on admission were associated with higher odds of in-hospital death (10). Moreover, subjects with most severe forms of COVID-19 illness commonly showed high levels of blood IL-6, high-sensitivity cardiac troponin I, lactate dehydrogenase and lymphopenia (10).

Based on our previous experience with a large number of patients affected by pneumonia from Covid19, we have observed that those subjects with a more severe prognosis might have some predictive markers. We intend to verify if these markers can identify those subjects with Covid19 infection who need a more intensive therapy and to find a prognosis score.

Methods

Before starting the study, the protocol will be submitted to and approved by the local Ethical Committees at the Fondazione Policlinico Universitario A. Gemelli IRCCS, Catholic University, Rome, Italy. Before enrollment each subject will sign the informed consent.

Inclusion criteria: subjects of both sexes aged 18 years or older consecutively hospitalized with diagnosis of pneumonia, confirmed by chest imaging, Covid-19 test positive, given informed consent to data collection from the patient.

Exclusion criteria: age lower than 18 years, pregnancy or breast-feeding.

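### If severe cases are few (about 10-15%), a sizeable share of the 200 half-sample logistic fits may have no finite estimate, and the plan has no rule for such fits

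*Combined protocol and SAP*

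**What the plan says.** Under Sample size calculation, the combined protocol and SAP takes a rule by which power for a medium-sized partial correlation "is approximately .80 if N = 104 + m, where m is the number of predictors". It assumes that "about 20 predictors will be evaluated for development of a risk score", so "the population size of the fitting population is set to N = 104+20=124 patients". Doubling for a 50/50 split gives the total: "A sample size of 248 patients will be therefore necessary". No expected event rate enters.

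Under Statistical Analysis, Primary Analysis, the outcome is coded 0/1 and the model is logistic by implication, through the definition of the C statistic. No penalty or exact method is named. Splitting, fitting and prediction are done 200 times. For each variable, "frequency histograms of the estimated coefficients along with their associated standard errors and levels of significance will be plotted", together with an importance index that is not defined. Then "the entire procedure is repeated on the subset of the most important variables", and the reduced model refitted to all patients becomes the score. No numerical selection criterion is given, and nothing is said about fits that do not converge.

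The only severity rates in the document are background figures in the Introduction, both from one cohort report: "49 (10.1%) severe cases at admission" among 487 patients, and progression in "15 out of 66 patients with a mild to moderate presentation of disease at admission".

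**The concern.** A logistic maximum-likelihood estimate is not finite when a predictor, or a combination of predictors, separates severe from non-severe patients. The simplest case is a yes/no predictor with an empty cell, for example when every severe case in the half has the symptom. Software then stops at an arbitrary large coefficient with a very large standard error, so coefficient divided by standard error is near 0 and the Wald p-value is near 1. Under complete separation this happens to every predictor, and the C statistic in the fitting half equals 1 by construction.

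With few events and about 20 predictors this can be frequent. The primary objective is to find the best predictors. If the 200 sets of coefficients, standard errors and significance levels mix real estimates with stopping-rule values, the stability check against the whole-sample estimates loses its meaning. A ranking built on Wald statistics could place a truly strong predictor low.

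**Working it through.** **1. The plan's own figures.** 104 + 20 = 124 and 2 x 124 = 248, as stated. The list under Primary end-point contains 19 single-term predictors. Seven are yes/no (cough, fever, dyspnea, diabetes, hypertension, ischemic heart disease, sex) and 12 are quantitative.

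**2. Events per half.** Using the two background rates as assumptions:
- 124 x 0.101 = 12.5 events; 12.5/20 = 0.6 per predictor.
- 124 x 15/66 = 28.2 events; 28.2/20 = 1.4 per predictor (28.2/19 = 1.5 for the listed 19).

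**3. A hand check of one empty cell.** Take a yes/no predictor with no effect and an assumed prevalence of 85%. The chance that every severe case has it is 0.85 to the power of the number of events: 0.85^12 = 14%, 0.85^18 = 5%, 0.85^28 = 1%. This is one variable only; other variables and combinations add to it.

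**4. Share of fits with no finite estimate.** Simulation with 7 yes/no and 12 quantitative predictors, latent correlation 0.2, and separation tested exactly by linear programming. Prevalences and effects are assumptions, because the document gives none. The first row uses 300 independent samples of 124 per setting. The others use 12 data sets of 248, each split 200 times.

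| Setting | 10.1% events | 15% | 22.7% | 30% |
|---|---|---|---|---|
| Independent samples, true C 0.5 to 0.9 | 33-73% | 14-36% | 4-14% | 1-4% |
| Splits, moderate effects | 49% | 28% | 6% | - |
| Splits, one yes/no predictor at OR 8 | 62% | 32% | 8% | - |
| Splits, one yes/no predictor at OR 20 | 77% | 72% | 20% | - |
| Splits, all yes/no at 50% prevalence | 24% | - | 0% | - |

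At 40% events the share is 0-1%. A separate run of the linear-programming check gave 43-60%, 14-33%, 1-9% and at most 4% at the four rates. The share also varies widely between data sets: 13% to 81% at 10.1% with moderate effects.

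**5. What happens to the p-values** (unpenalised fit, 25 iterations, Wald test):
- Complete separation: p > 0.9 for every predictor in 91-100% of such fits.
- Quasi-separation: p > 0.9 in 34-58% of such fits for the OR 8 predictor, 67-93% for the OR 20 predictor, and 34-99% for a null predictor at 85% prevalence.
- Over all 200 fits, at 10.1 / 15 / 22.7% events: p > 0.9 in about 35 / 13 / 5% for OR 8 and 62 / 67 / 14% for OR 20. For OR 8 at 10.1%, the parts are 0.378 x 0.01 + 0.467 x 0.44 + 0.155 x 0.92 = 0.35 (no, quasi- and complete separation).
- At 22.7% events, p < 0.05 still holds in about 92% of fits for OR 8 and 85% for OR 20.

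**6. Would another method do better?** In 400 simulated sets of 124 per setting, with one yes/no predictor at 50% prevalence and OR 12, the Wald test against Firth's penalised likelihood-ratio test had power 28% against 59% at 10.1% events, 65% against 83% at 15%, and 95% against 98% at 22.7%. At OR 6 or less and 22.7% events the two were about equal.

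**The case against.** The case against is substantial, and much of it stands.

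- **The low event rate is borrowed.** The 10.1% is severity at admission in another cohort. This study follows inpatients with pneumonia for up to 28 days, so progression during stay (15/66) is arguably the nearer analogue, and there the problem largely fades. This stands, although the plan states no rate at all.
- **Selection is not by p-value.** The importance index is undefined, and selection follows 200 splits and is not made on a single fit. In a simulation that assumed z-based importance (30 data sets per setting, 60 splits each), a predictor of OR 6-12 at 22.7% events ranked in the top 5 of 19 by median |z| in 97-100% of data sets. Demotion was common only at about 10-15% events with 70% prevalence, or at OR 30, which nothing in the document supports. This stands: demotion is a risk in particular settings.
- **There are partial safeguards.** Separated fits would show as extreme values in the histograms. The Secondary analyses add Fisher exact tests, PLS-DA and random forest, which do not need finite logistic estimates. But these are declared exploratory, and an extreme value in a plot is not a rule for handling it.
- **Firth is not the only remedy.** Ridge, lasso, likelihood-ratio tests or fewer predictors would also help, and Firth does not cure the shortage of events per predictor. This is fair; the point is that some method must be specified.

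A reader might infer that separation mainly strikes the strongest predictors. The calculations do not support that: a null predictor with very high prevalence is hit as well, and complete separation hits all of them. A reader might also infer that the stated power of .80 fails for larger effects. That figure is given for a medium-sized effect only, and the 95% at OR 12 with 22.7% events exceeds it.

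**Conclusion.** The point holds as a conditional gap in the primary analysis. The plan summarises 200 sparse logistic fits without stating the expected events or what is done when an estimate does not exist. At about 10-15% severe cases, roughly 15-75% of the fits could be affected (simulated range 14-77%, or about 28 to 154 of 200). At 22.7% the range is usually 0-14% (0 to 28 of 200), reaching about 20% only with one very strong yes/no predictor. At 30% or more it is at most about 4%. It would be wrong to say that many fits fail across the whole range of about 12 to 28 events, or that the plan will discard strong predictors. The shares rest on assumed event rates, prevalences, correlations and effects, and confidence in their exact size is moderate. The change is worth making because it protects the main result if events prove few and costs little if they do not.

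**What to change.** In the Primary Analysis:

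1. State that every logistic fit (the 200 splits, the whole-sample fit and the reduced model) uses a penalised likelihood, for example Firth's, with the usual intercept correction so that predicted probabilities match the observed event rate.
2. Take significance and the importance index from (penalised) likelihood-ratio tests and not from coefficient divided by standard error, and define the index.
3. State the expected number of severe cases. Report the observed number, and the number of the 200 splits that show separation.

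The cost is SAP wording and a standard software option, with no extra patients or data. The downside is slight shrinkage of coefficients towards zero and a slightly conservative test for weak predictors. In the simulations, apparent power was up to about 10 points below the ordinary test. The false-positive rate was 3-5% for the Firth test and up to 8% for the ordinary one.
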